3.4.3 Study Supplies Provided by Study Site

- Reference Control Article
- Treatment Material Disposition forms
- Product Washout Kits (toiletry items to be used by subjects during study)
- Consent / Authorization forms, IRB-approved
- Case Report Forms
- Sampling Solution, sterile
- Butterfield's sterile Phosphate Buffered Water containing neutralizers,
- High-purity deionized water, sterile
- Trypticase Soy Agar (TSA)
- Trypticase Soy Agar containing 0.5% Tween 80 and 0.07% lecithin (TSA+N)
- Transfer pipettes, polyethylene, sterile
- Serological pipettes
- Pipetting device, calibrated to accurately dispense 5.0 mL
- Tubes with sealable caps, polypropylene or glass, sterile
- Petri dishes, 100 mm, sterile

Page 13 of 53 Zurex Pharma, Inc. Project: ZX-ZP-0092 Microbac Protocol: 865.1.03.25.18

Microbac Project: 865-107

- Gloves, sterile
- Gauze, sterile (2" x 2")
- Marking templates, 5" x 5" & 1.5" x 5", sterile (for marking test sites)
- Non-toxic marking pen (Sharpie or equivalent)
- Rubber policemen, sterile
- Scrub cups
- Timers or stopwatches
- Pipette Aid or similar apparatus
- Vortex mixer
- Surgical Clipper & clipper blades
- Water bath (45° ± 2°C)
- Incubator (30° ± 2°C)
- Disposable underwear for subjects
- Tryptic Soy Broth (for the Neutralization Validation Procedure only See Appendix 14.10) (TSB)
- Urine Strip Test (for Pregnancy) or equivalent.

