5.2.3 Bacterial Enumeration Methods

Following sample collection, 10-fold serial dilutions will be prepared using Butterfield's Phosphate Buffered Water with

Page 24 of 53 Zurex Pharma, Inc. Project: ZX-ZP-0092 Microbac Protocol: 865.1.03.25.18

Microbac Project: 865-107

neutralizers (PBW). One mL aliquots of appropriate dilutions will be pourplated in triplicate using Trypticase Soy Agar containing neutralizers (TSA+N). Samples must be plated within 30 minutes of collection. After 72 \pm 4 hours of aerobic incubation at 30° \pm 2°C, colonies will be counted and viable cells in the original sample will be calculated according to Standard Operating Procedures. After incubation, plates may be refrigerated up to 48 hours prior to counting.

Raw colony counts from each dilution will be recorded on the appropriate data capture forms for each subject. The average number of microorganisms recovered (CFU/cm²) of skin for the screening and treatment day baseline samples will be calculated using the following formula to convert the plate CFU values into log₁₀ CFU/cm² of skin:

$$R = \log_{10} \left[\frac{F\left(\frac{\sum c_i}{n}\right)D}{A} \right]$$

Where:

R = the average CFU count in log_{10} scale per cm² of skin.

F = total mL of stripping fluid added to the sampling cylinder

 $\Sigma c/n$ = average of the triplicate colony counts for each sample collected

 $D = Dilution of the plates counted (10^0, 10^1, 10^2, 10^3, 10^4, or 10^5)$

A = Inside area of the sampling cylinder (

Dilution may be reported as dilution factor, which is the base 10 logarithm of the dilution. In that case, the factor of 'D' in the equation above will be replaced with 10^p.

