5.2.5 Neutralizer Validation

The effectiveness of the neutralizer system must be validated prior to the study start date to demonstrate that the antimicrobial is effectively neutralized and there is no effect on the growth of microorganisms. A procedure that will include in-vivo sampling will be combined with an in-vitro evaluation using procedures in accordance with ASTM E1054-08⁴ (2013). The procedure is Microbac - Confidential

Page 25 of 53 Zurex Pharma, Inc. Project: ZX-ZP-0092 Microbac Protocol: 865.1.03.25.18

Microbac Project: 865-107

attached as Appendix 14.10. These data must be provided in the final report.

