The treatments per subject will be randomized. The randomization scheme will be generated before the test.

4. Test Organisms

The test organisms for this study are:

- a.
- 5. Treatment Materials
 - a. ZuraPrep™ (containing 70% v/v Isopropyl Alcohol)
 - b. ChloraPrep® (reference control article containing 2% chlorhexidine gluconate)
 - c. ZuraPrep™ Vehicle (negative control article)
- 6. Materials, Supplies and Equipment

See section 3.4.3 of the Microbac 865-107 Protocol. In addition, 70% v/v isopropyl alcohol swabs.

7. In-vivo Test Procedures (collection of samples)

Preparation of Test Area and Post-Prep Sampling: Neutralization samples will be taken from the abdomen. The subject number, location of the prep application, location of the sites sampled within the prep area, and the time of sample collection will be documented on the appropriate data capture form. The subject will be treated with the study materials based on the following.

- For each side of the body, mark the abdominal test areas using a sterile 1.5" x
 5" template. The 1.5" x 5" areas will be delineated with each containing two 1" x 1" sampling site.
- After the test areas are marked, each area will be processed using three 70% isopropyl alcohol swabs for a total of one minute to prepare the site; the areas will be allowed to dry. This step is to prepare the skin for the neutralization test.
- Prep the test areas with the appropriate treatment according to the instructions provided in Appendix 14.7, Microbac 865-107 Protocol for groin.
- Using the scrub cup technique at approximately 30 seconds post-prep, begin collecting samples from each of two sampling sites within each test area using

Page 48 of 53 Zurex Pharma, Inc. Project: ZX-ZP-0092 Microbac Protocol: 865.1.03.25.18

Microbac Project: 865-107

SS by two technicians simultaneously. This technique is described in Section 5.2.1 of the Microbac 865-107 Protocol.

8.		ro Test Procedures (performed using the collected samples in accordance with ASTM 4-08 (2013))			
	8.1	Inoculur	m Preparation:		
		culture approxir such tha	th test organism, the organism will be prepared from and overnight broth $(24 \pm 4 \text{ hours})$ grown in TSB at $35 \pm 2\text{C}$ to yield a concentration of mately will be culture will be diluted using PBW in a manner will be delivered into the neutralizer tube (a aliquot bllected SS sample will be used).		
	8.2	Test:			

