		•	the reference to test article applies to test article, the vehicle and the ce control article; all procedures outlined, where applicable will employ all)		
		8.2.1	Neutralizer effectiveness (Test 1):		
		а	Out of the aliquot of sampling solution taken from the volunteer, will be transferred to a new sterile tube and inoculated with the challenge microorganism so that the final concentration will equal colony-forming units (CFU) / mL of the challenge microorganism (the prepared inoculum will be diluted using PBW to achieve the desired concentration, aliquot from the dilution will be used).		
		b	Within one min after the addition of the challenge microorganism, the microorganisms will be enumerated by standard microbiological methods extant in the laboratory.		
		С	Triplicate aliquots will be removed and plated using TSA+N pour plates.		
		d	After 30 minutes, the microorganisms will be enumerated a second time using the same procedures.		
		е	Triplicate aliquots will be removed and plated using TSA+N pour plates.		
		8.2.2	Neutralizer toxicity (Test 2):		
		а	A aliquot of sampling solution will be inoculated with the challenge microorganism so that the final concentration will equal colony-		

manner as Test 1.

forming units (CFU) / mL of the challenge microorganism in the same

Page 49 of 53 Zurex Pharma, Inc. Project: ZX-ZP-0092 Microbac Protocol: 865.1.03.25.18 Microbac Project: 865-107

- b Within one min after the addition of the challenge microorganism, the microorganisms will be enumerated by standard microbiological methods extant in the laboratory.
- c Triplicate aliquots will be removed and plated using TSA+N pour plates.
- d After 30 minutes, the microorganisms will be enumerated a second time using the same procedures.
- e Triplicate aliquots will be removed and plated using TSA+N pour plates.
- f This procedure will be repeated two times for a total of three replicates.

8.2.3 Test microorganism viability control (Test 3):

- a A aliquot of PBW will be inoculated with a volume of the challenge microorganism so that the resulting suspension contains CFU/mL in the same manner as Test 1.
- b Within one min the microorganisms will be enumerated (in triplicate) by standard microbiological methods extant in the laboratory.
- c Triplicate mL aliquots will be removed and plated using TSA pour plates.
- d After 30 minutes, the microorganisms will be enumerated a second time using the same procedures.

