- e Triplicate aliquots will be removed and plated using TSA pour plates.
- This procedure will be repeated two times for a total of three replicates.

8.2.4 Test article control (Test 4):

- a A aliquot of the test or control article will be inoculated with a volume of the challenge microorganism so that the resulting suspension contains CFU/mL in the same manner as Test 1.
- b Within one min the microorganisms will be enumerated (in triplicate) by standard microbiological methods extant in the laboratory.
- c Triplicate mL aliquots will be removed and plated using TSA pour plates.
- d After 30 minutes, the microorganisms will be enumerated a second time using the same procedures.

Page 50 of 53 Zurex Pharma, Inc. Project: ZX-ZP-0092 Microbac Protocol: 865.1.03.25.18

Microbac Project: 865-107

е	Triplicate	mL aliquots	will be	removed	and	plated	using	TSA	pou
	plates.								

f This procedure will be repeated two times for a total of three replicates.

8.3 Incubation:

All plates for Tests 1, 2, 3 and 4 will be incubated for 72±4 hours at 30°±2°C.

8.4 Interpretation of data:

- a. The number of surviving challenge microorganisms for each replicate from each test will be average count of the three plates.
- b. The number of survivor values will be transformed to log₁₀.
- c. The number of survivors (log₁₀) from each test (1, 2, and 4) will be compared to the test microorganism viability population (test 3).
- d. Neutralization aspects of the sampling solution will be considered adequate if the mean log₁₀ CFU/mL of Test 1 is not more than 0.20 log₁₀ less than the mean log₁₀ CFU/mL of Test 3 (Mean log₁₀ CFU/mL from Test 3 Mean log₁₀ CFU/mL from Test 1 using corresponding time points).
- e. The sampling solution will be considered non-toxic if the mean \log_{10} CFU/mL of Test 2 is not more than 0.20 \log_{10} less than the mean \log_{10} CFU/mL of Test 3 (Mean \log_{10} CFU/mL from Test 3 Mean \log_{10} CFU/mL from Test 2 using corresponding time points).
- f. The mean log₁₀ CFU/mL from Test 4 must be at least 0.20 log₁₀ less than the mean log₁₀ CFU/mL of Test 3.
- g. The amount of CFU added for each aspect must be confirmed to yield a final suspension containing CFU/mL (validated in test 3).
- h. The sterility controls must be negative for growth.

8.5 Controls:

8.5.1 Sterility control:

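### As written, the viability control in the neutralizer validation (Test 3) uses a buffer defined as containing neutralizers, so suspension-phase toxicity that it shares with the sampling solution is masked

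*Combined protocol and SAP*

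**What the plan says.** - **Purpose.** Section 5.2.5 requires the validation, before study start, to show that the antimicrobial is neutralized and that "there is no effect on the growth of microorganisms".
- **Meaning of PBW.** Section 5.2.3 states "10-fold serial dilutions will be prepared using Butterfield's Phosphate Buffered Water with" and, across a page break, continues "neutralizers (PBW). One mL aliquots of appropriate dilutions". The abbreviation thus belongs to the buffer with neutralizers. The supply list in 3.4.3 has one Butterfield's buffer: "Butterfield's sterile Phosphate Buffered Water containing neutralizers".
- **Materials for the validation.** Appendix 14.10, item 6: "See section 3.4.3 of the Microbac 865-107 Protocol. In addition, 70% v/v isopropyl alcohol swabs". No plain Butterfield's buffer is added.
- **Test 2 (toxicity), 8.2.2.** "A aliquot of sampling solution will be inoculated with the challenge" organism; plated on TSA+N.
- **Test 3 (viability control), 8.2.3.** "A aliquot of PBW will be inoculated with a volume of the challenge microorganism"; plated on plain TSA.
- **Inoculum.** Items 8.1 and 8.2.1 dilute it in PBW, and Tests 2 to 4 follow the manner of Test 1.
- **Acceptance, 8.4.** Test 3 is the reference for Tests 1, 2 and 4. On toxicity (8.4e): "The sampling solution will be considered non-toxic if the mean" log10 count of Test 2 falls no more than 0.20 below that of Test 3. Criterion 8.4d applies the same limit to Test 1. Criterion 8.4g confirms the inoculum level within Test 3.

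**The concern.** A viability control should show how many cells survive when no neutralizer is present. Plating Test 3 on plain TSA fits that aim, but suspending it in PBW, as the protocol defines PBW, does not. If the sampling solution and PBW harm cells in the same way during suspension, Tests 2 and 3 fall together and criterion 8.4e does not see the loss.

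What is at stake is the validity of the recovery method. Samples may wait up to 30 minutes before plating (5.2.3), which is also the holding time tested in 14.10. Every count in the trial passes through this system, including the baseline counts that decide eligibility and per-protocol membership. A hidden loss would lower those counts while the validation report declared the system non-toxic.

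**Working it through.** The plan gives no figure to reproduce here. The check is algebra on criterion 8.4e, followed by a simulation of its pass rate.

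**Inputs from the documents:** fluids and agars as listed above; three replicates each for Tests 2 and 3; three plates per replicate, averaged and then log-transformed; limit 0.20 log10.

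**Assumed, because the documents do not show them:** 30, 60 or 100 CFU per plate in the absence of any loss; a true suspension loss in the sampling solution of 0.3, 0.5 or 1.0 log10; the share of that loss that PBW also causes (none, half, all); an agar loss of 0 or 0.3 log10.

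**Step 1: the limit.** 10^-0.20 = 0.631, so the criterion tolerates a loss of 36.9% of cells. For comparison, 0.5 log10 is 1 - 10^-0.5 = 68%.

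**Step 2: what is compared.** Let N be the log10 inoculum after dilution, and t the log10 loss from each source.

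- Test 3 = N - t_PBW
- Test 2 = N - t_SS - t_agar
- Test 3 - Test 2 = (t_SS - t_PBW) + t_agar

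Loss common to the two fluids cancels; agar loss does not. Any loss while the inoculum is diluted in PBW is already inside N for both tests and cancels as well.

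**Step 3: how much overlap is needed.** If PBW causes a share s of the sampling solution's loss and t_agar = 0, the expected difference is (1 - s) × t_SS. It is within 0.20 when s ≥ 1 - 0.20/t_SS:

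- t_SS = 0.3: s ≥ 0.33
- t_SS = 0.5: s ≥ 0.60
- t_SS = 1.0: s ≥ 0.80

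**Step 4: simulated chance of passing 8.4e.** Poisson plate counts, 40,000 runs per setting. Every setting has a true loss above the limit, so every pass is a false pass.

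| True loss in sampling solution | PBW share | Agar loss | Expected difference | Pass at 30 / 60 / 100 CFU |
|---|---|---|---|---|
| 0.3 | all | 0 | 0 | 100 / 100 / 100% |
| 0.3 | half | 0 | 0.15 | 83.6 / 92.0 / 96.7% |
| 0.3 | none | 0 | 0.30 | 1.2 / 0.1 / 0.0% |
| 0.5 | all | 0 | 0 | 99.8 / 100 / 100% |
| 0.5 | half | 0 | 0.25 | 18.9 / 11.0 / 5.6% |
| 0.5 | none | 0 | 0.50 | 0 / 0 / 0% |
| 1.0 | all | 0 | 0 | 93.7 / 98.8 / 99.9% |
| 1.0 | half | 0 | 0.50 | 0 / 0 / 0% |
| 0.3 | all | 0.3 | 0.30 | 5.4 / 1.3 / 0.2% |
| 0.5 | all | 0.3 | 0.30 | 9.8 / 3.6 / 1.1% |
| 1.0 | all | 0.3 | 0.30 | 22.0 / 14.8 / 9.2% |

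The rows with a PBW share of none show how the criterion behaves with a neutralizer-free reference: the false-pass rate is at most 1.2% at 0.3 log10 and zero in the simulation at 0.5.

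**The case against.** **The validation is not blind to toxicity.** This stands. Tests 1 and 2 are plated on TSA+N and incubated for 72 hours, against about 30 minutes in suspension. If the agar adds a 0.3 log10 loss, the pass rate drops to between 0.2 and 22% even with full overlap. A reader might infer that shared neutralizer toxicity cannot be detected at all; the plain TSA plates in Test 3 rule that out.

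**The overlap is unknown.** This stands too. The sampling solution's composition is not visible and no ingredients are named for PBW. Complete cancellation is only the full-overlap case, and at half overlap a 0.5 log10 loss would usually be caught.

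**Other checks exist.** This stands only in part. Criterion 8.4g might expose a gross loss in Test 3, but it is measured in the same PBW and its target is not visible. The growth promotion control in 5.2.4 examines TSA+N agar, not the suspending fluids.

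**Antiseptic carryover is still detected.** Correct. With carryover c, Test 3 - Test 1 = (t_SS - t_PBW) + t_agar + c, and Test 3 contains no antiseptic. A lowered Test 3 makes 8.4d easier to pass, but the weakness is mainly about toxicity.

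**It may be only an ambiguous abbreviation.** Possible. Plain TSA in Test 3 suggests that a plain buffer was meant. But then one abbreviation covers two fluids, and the plain one is missing from the supply list that the appendix adopts.

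**Inflated efficacy.** A reader might infer that the superiority contrast or the 6-hour comparison is inflated because neutralizers harm antiseptic-stressed cells more. Nothing in the documents supports this. A uniform proportional loss would largely cancel between arms. All the tests use an overnight broth culture, so a plain-buffer Test 3 would not measure such an effect either.

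**Conclusion.** The point holds for toxicity that acts in suspension and is common to PBW and the sampling solution. Followed as written, the procedure has no neutralizer-free count, and criterion 8.4e can pass a recovery system whose loss exceeds the 0.20 log10 limit. The size depends on the overlap: a 0.5 log10 loss would pass almost always with full overlap and in about 6 to 19% of runs with half overlap. Both figures assume 30 to 100 CFU per plate and no agar toxicity.

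The documents show that a false pass is possible. They do not show that the sampling solution is toxic, that a false pass has occurred, or that any treatment contrast is biased. The plan should be corrected because Section 5.2.5 asks for a proof that this control cannot fully give, and because the remedy is small.

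**What to change.** 1. In Appendix 14.10, section 8.2.3, run Test 3 in neutralizer-free Butterfield's buffer and dilute its inoculum in that same buffer. Keep the TSA plates. Test 2 is best inoculated from the same preparation, so that both tests start from one count.
2. Give the plain buffer and the buffer with neutralizers different abbreviations throughout, and add the plain buffer to 3.4.3.
3. If the validation has already been run, first establish from the laboratory record which buffer Test 3 used. If it was neutralizer-free, correcting the text is enough. If it contained neutralizers, repeat Tests 2 and 3 with the plain-buffer control to re-evaluate criterion 8.4e.

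**Cost.** One additional buffer and an edit to the appendix and supply list. Repeating Tests 2 and 3 is bench work without subjects. Re-evaluating criterion 8.4d against a concurrent plain-buffer reference would be more costly, because Test 1 needs new samples from treated volunteers. The downside is that the toxicity criterion becomes harder to meet.

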14.11 Skin Irritation Rating Scale

	Skin Irritation Rating Scale Reactive area(s) within the treatment site only				
Condition	Rating	Description			
	0	No reaction			
Em the area	1	Mild and/or transient redness			
Erythema	2	Moderate redness			
	3 ^a	Severe redness			
	0	No reaction			
Edomos	1	Mild and/or transient swelling			
Edema	2	Moderate swelling			
	3ª	Severe swelling			
	0	No reaction			
Rash	1	Mild and/or transient rash			
Rasn	2	Moderate rash			
	3ª	Severe rash			
	0	No reaction			
Drugge	1	Mild and/or transient dryness			
Dryness	2	Moderate dryness			
	3ª	Severe dryness			

^a = A rating of 3 on the skin irritation scale in any category will be recorded as Adverse Event and will require subject's removal from the study.

Page 53 of 53 Zurex Pharma, Inc. Project: ZX-ZP-0092 Microbac Protocol: 865.1.03.25.18

Microbac Project: 865-107

14.12 Estimation of Sample Size Report

See attached report.

14.13 Informed Consent Forms

See attached forms.
